5.3 Demographics and Baseline Characteristics

Baseline variables (e.g., age, ethnic origin) will be summarized descriptively by treatment group. For each continuous variable, the summary will include the mean, standard deviation, minimum and maximum. For each categorical variable, the summary will include frequencies and percentages.

5.4 Subject Accountability

A summary of subject disposition will be provided for all subjects. Descriptive summaries of subject disposition, reason for discontinuation, and analyses population will be provided by treatment group. The data will also be presented in subject data listings.

5.5 Efficacy Variables and Analyses

5.5.1 Primary Endpoint

The primary endpoint of the study is the proportion of subjects identified as responders at Visit 3/End of Study. A responder is defined as a subject with at least a 25% reduction from baseline (Visit 1/Screening) in the sum of % (percent) basal/parabasal + % (percent) intermediate cells on vaginal cytology AND vaginal pH < 5.0 with a change from Visit 1/Screening vaginal pH of at least 0.5.

Equivalent Efficacy

The compound hypothesis to be tested for clinical equivalence between test and reference is:

$$H_0$$
: $p_T^- p_R^- < -0.20$ or $p_T^- p_R^- > 0.20$ versus

$$\boldsymbol{H}_{\boldsymbol{A}}$$
: -0.20 $\leq \boldsymbol{p}_{\boldsymbol{T}}$ - $\boldsymbol{p}_{\boldsymbol{R}} \leq 0.20.$

Where p_T and p_R are the proportions of responders at Visit 3/End of Study (Day 8) for the test and reference products, respectively. The test product will be considered to be clinically equivalent to the reference product if the 90% CI on the difference in their proportions of responders, calculated by the Wald's method with Yates' continuity correction, is contained within the limits -0.20 to +0.20. Rejection of the null hypothesis supports the conclusion of therapeutic equivalence between the test and reference products for the primary efficacy variable.

Analysis for bioequivalence will be performed based on the following SAS code (SAS Institute v.9.1.3):

P-value is chosen from Continuity Adj. Chi-Square test.

The SAS code for 90% confidence interval (trt=1 for Test, trt=2 for Reference): proc freq data=XX;

```
where trt in (1,2);
tables trt* success / alpha=0.10 riskdiff;
output out=CIDIFF (keep= l_rdif2 u_rdif2 ) riskdiff;
run;
```

For the final 90% continuity-corrected CI, the lower limit = $(1_rdif2 - yates)$ and the upper limit = $(u_rdif2 + yates)$, where yates, the Yates' continuity-correction factor, is derived as (1/n1+1/n2)/2, n1=number of subjects in Test arm and n2=number of subjects in Reference arm.

Superiority

The hypotheses to be tested for superiority of the test and reference products over Vehicle are:

$$H_0: p_T \le p_V \text{ versus } H_A: p_T > p_V$$

$$H_0: p_R \le p_V \text{ versus } H_A: p_R > p_V$$

Where p_T , p_R and p_V are the proportions of responders at Visit 3/End of Study (Day 8) for the test, reference and Vehicle products, respectively. The tests will be conducted independently for the test product and the reference product using two-sided, $\alpha = 0.05$, continuity-corrected Z-tests. Superiority will be established if the proportion of responders in the active treatment group is greater and statistically different (P \leq 0.05) than that in the Vehicle. Rejection of the null hypothesis supports the conclusion of superiority of the test and reference products over the Vehicle product for the primary efficacy variable.

Superiority analyses will be conducted on both the mITT and the PP populations.

Analysis for bioequivalence will be performed based on the following SAS code (SAS Institute v.9.1.3):

```
The SAS code for p-value (trt=2 for Reference vs. trt=3 for Vehicle): proc freq data=XX; where trt in (2,3); table trt * success /chisq; run;
```

In the mITT population, a LOCF approach will be used to impute missing efficacy data. PP subjects who discontinue due to treatment failure will be included as non-responders for the primary endpoint. No formal statistical analyses are planned to evaluate the consistency of efficacy results across the multiple centers for the primary efficacy variable. These results, however, will be tabulated and, if a center's response is obviously inconsistent with those of the other centers, this will be explored and addressed in the final study report.

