5.1 Methodological Considerations

All randomized subjects who received study medication will be evaluated for safety. The efficacy analysis will be conducted on both the PP and the mITT populations. No adjustments of p-values for multiple comparisons will be made. No interim analyses are planned. Two-sided hypothesis testing will be conducted for all the tests. Resulting p-values \leq than 0.05 will be considered statistically significant unless noted otherwise. SAS software will be used for all data analyses and tabulations.

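### The primary comparisons are valid but take no account of Visit 1 pH and cytology, so some precision may be lost and a baseline difference created by PP selection would go uncorrected

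*SAP*

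**What the plan says.** SAP 5.5.1 defines the endpoint: "The primary endpoint of the study is the proportion of subjects identified as responders at Visit 3/End of Study". A responder needs "at least a 25% reduction from baseline (Visit 1/Screening) in the sum of % (percent) basal/parabasal + % (percent) intermediate cells" and also "vaginal pH < 5.0 with a change from Visit 1/Screening vaginal pH of at least 0.5". Both Visit 1 measurements are therefore required to classify a subject by change from baseline.

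For Test versus Reference, the 90% interval for the difference in proportions is "calculated by the Wald's method with Yates' continuity correction", and equivalence is concluded if it "is contained within the limits -0.20 to +0.20". The code is a two-way table, "tables trt* success / alpha=0.10 riskdiff", widened on each side by half of (1/n1 + 1/n2). For Test and Reference against Vehicle, section 5.5.1 specifies two-sided "continuity-corrected Z-tests" at 0.05, coded as a chi-square on the same kind of table. No covariate, stratum or adjusted sensitivity analysis appears.

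Section 5.1 adds: "The efficacy analysis will be conducted on both the PP and the mITT populations". Section 4 forms the PP set partly on events after randomization: prohibited medication, significant violations, the Visit 3 window, endpoint data and compliance. Section 5.3 summarises baseline variables descriptively, with age and ethnic origin named only as examples.

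**The concern.** The responder rule gives a structural reason to expect starting pH to matter. If the pH change is read as a fall, a subject must drop at least 0.5 and end below 5.0. Up to a Visit 1 pH of 5.0 + 0.5 = 5.5, the 0.5 change is the binding condition. Above 5.5 the fixed threshold binds, and the required fall grows one for one with starting pH. How strongly this predicts response is not stated and cannot be taken from the SAP.

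Two things could follow. If baseline is prognostic, the intervals and tests are wider or weaker than they need be, using data already required for the endpoint. In the PP set, where exclusions after randomization could leave the arms different at baseline, an unadjusted difference would carry that imbalance into the equivalence decision, and no planned analysis would show how much it mattered.

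**Working it through.** **Inputs.** From SAP 5.5.1: limits of ±0.20, a 90% interval, and Yates factor (1/n1 + 1/n2)/2. Arm sizes, allocation ratio, response rates and power cannot be read in section 3.2, so there is no stated figure to reproduce. Assumed instead: equal Test and Reference arms of n, response rate p = 0.5 in both, true difference 0.

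**Step 1: the planned rule.** With equal arms the Yates factor is 1/n.

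- se = √(2p(1−p)/n)
- half-width = 1.645·se + 1/n
- power = 2Φ((0.20 − half-width)/se) − 1

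At n = 150: se = √(0.5/150) = 0.0577; half-width = 0.0950 + 0.0067 = 0.102; power = 2Φ(1.704) − 1 = 0.912.

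**Step 2: the same rule with the variance cut by a fraction v.** Replace se by se·√(1−v) and keep the Yates factor. At n = 150 and v = 0.10: se = 0.0548; half-width = 0.0901 + 0.0067 = 0.097; power = 0.941.

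| n per arm | v = 0 | v = 0.05 | v = 0.10 | v = 0.20 |
|---|---|---|---|---|
| 100 | 0.703 | 0.734 | 0.765 | 0.826 |
| 150 | 0.912 | 0.927 | 0.941 | 0.964 |
| 200 | 0.976 | 0.982 | 0.986 | 0.993 |

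**Step 3: what v might be.** A simulation compared the crude difference with a logistic g-computation difference adjusted for one standard normal baseline covariate (1,500 runs, 150 per arm, about 50% response, no treatment effect). The third and fourth columns give the mean crude difference when the arms differ systematically at baseline by 0.1 or 0.2 SD; the true value is 0.

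| log-odds per SD | variance cut, no shift | crude bias, 0.1 SD | crude bias, 0.2 SD |
|---|---|---|---|
| 0 | about 0% | 0.001 | 0.000 |
| 0.3 | 2% | 0.006 | 0.014 |
| 0.6 | 5% | 0.015 | 0.027 |
| 1.0 | 17% | 0.020 | 0.041 |

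The adjusted estimate stayed within 0.002 of 0 throughout. Without a shift the crude estimate was within 0.003 of 0. The Monte Carlo standard error of these means is about 0.058/√1500 = 0.0015.

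A second simulation, with latent correlations of 0.2 to 0.5 between baseline pH and response and with baseline pH assumed to lie above 5, gave variance ratios of 0.97 to 0.85, which is a cut of 3% to 15%.

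**Step 4: separating adjustment from the Yates term.** At p = 0.5 and true difference 0:

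| n per arm | planned rule | 8% variance cut, Yates kept | no adjustment, Yates dropped |
|---|---|---|---|
| 125 | 0.836 | 0.871 | 0.871 |
| 150 | 0.912 | 0.935 | 0.931 |

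Dropping the continuity correction alone gives about the same rise in power as an 8% cut in variance. A comparison of intervals therefore isolates adjustment only if both carry the Yates widening.

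**Step 5: superiority.** No power can be given, because arm sizes and the Vehicle rate are unreadable. A variance cut v shrinks the standard error by 1 − √(1−v): 2.5% at v = 0.05 and 8.9% at v = 0.17. The values of v were simulated at 50% response and may differ for a Vehicle arm with few responders.

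**The case against.** The strongest reply is that nothing here is wrong. The hypotheses concern the marginal difference in proportions. The crude difference estimates exactly that, the Yates factor is the standard one, and the SAP nowhere promises an adjusted analysis. All of this stands. The gain also rests on assumed prognostic strength, and that stands too.

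A reader might infer that the crude PP result is biased. The SAP does not support that. Chance imbalance is already covered by the interval; only systematic imbalance from selection would bias the result, and none is shown. Adjusting for pH and cytology would not remove selection on unmeasured factors. The mITT analysis is run alongside, although that set also requires a post-randomization assessment.

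A reader might also infer that an adjusted interval should replace the planned one for equivalence. Step 4 shows the difficulty: an interval without the Yates widening would remove a deliberate conservatism from the decisive rule, and the apparent gain would not come from adjustment alone.

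Neither reply rules out adjusted superiority tests, which have no margin, or an adjusted equivalence interval shown beside the planned one. A standardised risk difference targets the same p_T − p_R against the same ±0.20 limits. One caution carries over: an adjusted superiority test with a robust standard error also omits a continuity correction, so the planned Z-tests should stay visible. Finally, that both Visit 1 values exist for all analysed subjects is inferred from the responder definition, because the schedule in section 6.2 could not be read in the copy reviewed.

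**Conclusion.** The point holds as a low-severity improvement. The three primary comparisons are valid and internally consistent, but they leave unused two baseline values that the endpoint itself requires. The possible cost is about 0 to 17% of variance. At p = 0.5, true difference 0 and 150 per arm, a cut of 5% to 20% would add about 1.5 to 5 percentage points of equivalence power; at 100 per arm, a 20% cut would add about 12 points. If baseline is not prognostic the gain is nil. A systematic PP imbalance of 0.1 to 0.2 SD, if it occurred and baseline were prognostic, would move the crude difference by about 0.006 to 0.041; the upper end is about a fifth of the 0.20 margin. All these sizes rest on assumed arm sizes, response rates and prognostic strength.

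**What to change.** Set the following in section 5.5.1 before unblinding.

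- **Superiority:** test Test versus Vehicle and Reference versus Vehicle with a standardised (g-computation) risk difference from a logistic model containing treatment, Visit 1 pH and the Visit 1 sum of percent basal/parabasal and percent intermediate cells, with a robust standard error. Keep the continuity-corrected Z-tests as sensitivity analyses.
- **Equivalence:** keep the planned Yates-corrected 90% Wald interval as decisive. Beside it, in both PP and mITT, report the adjusted 90% interval for the same p_T − p_R against −0.20 to +0.20, widened by the same Yates factor, so that any difference reflects adjustment only.
- **Fallback:** state in advance that the unadjusted test is used if the model does not converge, for example with few Vehicle responders.
- **Baseline table:** name Visit 1 pH and the cytology sum by arm, for mITT and PP, in section 5.3, which does not exclude them now.

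The cost is SAP wording and a short extra program, with no new data. The downside is an analysis slightly less simple than a two-by-two table.

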5.5.2 Secondary Endpoints

The secondary endpoint will be the proportion of subjects with treatment success based on the improvement (change from baseline (Visit 2/Randomization)) of the Most Bothersome Symptom (MBS) of VVA at Visit 3/End of Study. Treatment success is defined as a change

from baseline which results in a score of 0 (none) or 1 (mild) at Visit 3 if the MBS is vaginal dryness, vaginal or vulvar irritation or itching, dysuria and vaginal pain associated with sexual activity. If the MBS is vaginal bleeding associated with sexual activity then treatment success will be absence of vaginal bleeding associated with sexual activity as reported at the end of the study. The same methods of analysis as for the primary analyses will be conducted for the secondary endpoint.

5.6 Safety Variables and Analyses

Duration of Treatment and Medication Compliance

Number of applications, days of exposure, and compliance rate will be summarized by treatment group using descriptive statistics. For each subject, the overall duration of treatment (days) will be calculated using the following formula:

(Date of last application of study medication) - (Date of first application of study medication) + 1.

Medication compliance rate (%) will be calculated for each subject as follows:

(Total number of applications used) / (Expected number of applications) *100%.

Subjects who complete the study are expected to have 7 applications. For prematurely discontinued subjects, expected number of applications will be determined based on the expected number of applications by the time of discontinuation, i.e. the overall duration of treatment. Descriptive summaries of exposure and medication compliance rate will be provided by treatment group for the ITT subjects.

Adverse Events

Adverse events (AEs) will be coded in MedDRA, version 18.1. Treatment-Emergent Adverse Event (TEAE) is defined as any AE occurs on or after application of the first dose of study drug. Number and percent of subjects reporting TEAEs will be tabulated by treatment group. Summaries will be presented by body system and preferred term for the ITT population, and further by severity and relationship to study medication. TEAEs reported by 5% or more subjects for any treatment group will also be summarized. In the summaries of incidence rates (frequencies and percentages) by severity and relationship to study drug, subjects who report more than one event that are mapped to the same preferred term will be counted only once under the strongest severity and relationship, accordingly. Chi-Square or Fisher's exact test will be used to compare the proportions of subjects of the two active treatment groups who report any TEAE.

Treatment-Emergent Serious Adverse Events (TESAEs) will be discussed within the clinical study report. TEAEs, TESAEs and TEAEs that led to treatment interruption or discontinuation will be presented in data listings.

Concomitant Medications, Laboratory Values, and Vitals Signs

Concomitant medications will be coded using the WHO Drug Dictionary, version September 2015, and will be presented in data listings. All laboratory data and vital signs data will be displayed in listings.

Safety comparisons will be performed only for the ITT population.

6 Appendices

6.1 Handling of Missing or Incomplete Dates for Adverse Events and Concomitant Medications

Adverse Events

Handling of partial dates is only considered for the start date. An adverse event with a partial start date is considered treatment emergent if:

- only the day is missing and the start month/year is the same or after the month/year of the first dose
- the day and month are missing and the start year is the same or greater than the year of the first dose date
- the start date is completely missing

Concomitant Medications

Handling of partial dates is only considered for the stop date. A medication with a partial stop date is considered concomitant if:

- only the day is missing and the stop month/year is the same or after the month/year of the first dose
- the day and month are missing and the stop year is the same or greater than the year of the first dose date
- the stop date is completely missing or the medication is ongoing

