3.1 Study Design

The study will be conducted as a double-blind, randomized, parallel-group, vehicle-controlled, multicenter trial.

Each subject will be randomly assigned to one of following treatment groups

s :

- (1) Test: Estradiol Vaginal Cream 0.01%,
- (2) Reference: ESTRACE (estradiol) Vaginal Cream, USP, 0.01%, manufactured by Warner Chilcott (US), LLC
- (3) Vehicle: Vehicle of the test product,

Subjects will be admitted into the study only after written informed consent has been obtained and all of the inclusion and none of the exclusion criteria have been met. Randomization will be performed according to a computer generated randomization scheme where the treatment group designation has been assigned to the subject number. The treatment designation will remain blinded until after the final database is locked. An independent third party generator will generate and hold the randomization code throughout the study. Randomized subjects will apply 2 grams of the assigned treatment once daily intravaginally at bed time for 7 days at approximately the same time each day.

Subjects will come to the study site for clinical evaluations at Visit 1/Screening (Day -14 to Day -1), Visit 2/Randomization (Day 1), and Visit 3/End of Study (Day 8, +3 days) or at early discontinuation.

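### Section 6.1 can count an AE as treatment-emergent although its recorded stop date is before first dose

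*SAP*

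**What the plan says.** Section 5.6 (Adverse Events) gives the definition: "Treatment-Emergent Adverse Event (TEAE) is defined as any AE occurs on or after application of the first dose of study drug".

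Section 6.1 supplies the rule for incomplete dates. It limits itself at the outset: "Handling of partial dates is only considered for the start date". An AE is then treatment-emergent under any one of three conditions:

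- Month and year recorded: "only the day is missing and the start month/year is the same or after the month/year of the first dose".
- Year alone recorded: it equals or follows the year in which dosing began.
- No part of the start recorded: always treatment-emergent.

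None of the three refers to the stop date.

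TEAE status feeds the tables by body system and preferred term, the breakdowns by severity and relationship, the summary of events at 5% or more, the serious-event discussion and the listings. It also feeds one formal test in Section 5.6: "Chi-Square or Fisher's exact test will be used to compare the proportions of subjects of the two active treatment groups who report any TEAE".

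**The concern.** When the onset date is uncertain, counting the AE as treatment-emergent is a common and defensible convention. A stop date before first dose removes the uncertainty: wherever the onset lay, the event was over before exposure. Section 6.1 still classes such an AE as treatment-emergent if its start is missing or its known part coincides with the month or year of first dose. A programmer who follows the appendix as written gets a result that the recorded data refute and that the Section 5.6 definition excludes.

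At stake is the accuracy of the TEAE counts in each arm, and of the any-TEAE comparison between the two active products. Each such error adds an event and none removes one.

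**Working it through.** The SAP states no figure on this point, so there is none to reproduce. The check applies the two rules to the same records and then asks how easily a pre-dose AE meets the Section 6.1 conditions.

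**Step 1: the rules side by side.** Illustrative dates: first dose 15 March 2016, AE stop date 10 March 2016. Because the AE ended before dosing, it cannot satisfy Section 5.6 ("any AE occurs on or after application of the first dose of study drug") in any row.

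| Recorded start | Section 6.1 | Section 5.6 | Agree? |
|---|---|---|---|
| none | TEAE | not a TEAE | no |
| March 2016 (day missing) | TEAE | not a TEAE | no |
| 2016 (day and month missing) | TEAE | not a TEAE | no |
| February 2016 (day missing) | not a TEAE | not a TEAE | yes |
| 2015 (day and month missing) | not a TEAE | not a TEAE | yes |

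The conflict is confined to the first three rows. A partial start before the month or year of first dose meets none of the three conditions and is already left out.

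**Step 2: how often a screening-period onset falls into those rows.** Input: Section 3.1 places screening at Day -14 to Day -1 and randomization on Day 1. Assumptions: first dose on Day 1, first-dose dates spread evenly over a 365-day year, and onset spread evenly over the screening window.

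An onset k days before first dose lies in an earlier month only if first dose falls on one of the first k days of a month, which is 12k days in the year. It lies in an earlier year only if first dose falls on one of the first k days of the year. Hence:

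- share in the same month and year = 1 - 12k/365
- share in the same year = 1 - k/365

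Averaging over k = 1 to L replaces k by (L + 1)/2.

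| Screening length L | Mean k | Day missing: same month | Day and month missing: same year |
|---|---|---|---|
| 1 day | 1 | 1 - 12/365 = 96.7% | 1 - 1/365 = 99.7% |
| 7 days | 4 | 1 - 48/365 = 86.8% | 1 - 4/365 = 98.9% |
| 14 days | 7.5 | 1 - 90/365 = 75.3% | 1 - 7.5/365 = 97.9% |

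A direct count over the calendar years 2015 to 2018 gave 96.7%, 86.9% and 75.4% for the same month, which agrees. With no start date the share is 100% by rule.

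An AE that resolved before dosing tends to have started earlier in the window, so the same-month share for such AEs may be lower. At k = 14 it is 1 - 168/365 = 54.0%.

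These shares apply only once an AE with onset in screening and an incomplete start date exists. They are not an incidence.

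**Step 3: effect on the any-TEAE comparison.** Let q be the share of otherwise TEAE-free subjects in each arm who are wrongly counted. An arm's proportion p becomes p + q(1 - p), so the difference between arms becomes (1 - q)(p_T - p_R). The SAP gives no value for q. To show the shape only, q = 1.5% would turn a 10-point difference into 0.985 x 10 = 9.85 points.

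**The case against.** The strongest reply is that the opening sentence of Section 6.1 says which partial dates get a handling rule, not that a complete stop date is to be ignored. On that reading Section 5.6 still governs, and only a clarification is missing. But the SAP nowhere says that the definition overrides the three conditions, and those conditions are stated as sufficient. The same appendix does use the stop date for concomitant medications: one with a partial stop before the month or year of first dose meets none of its conditions.

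The points on size stand. The problem needs several things together: an AE within at most 14 days of screening, resolved before dosing, with a usable stop date and an incomplete or absent start date. Such events precede exposure, so randomization balances them between arms in expectation. A subject's any-TEAE status changes only if she has no genuine TEAE. Step 3 shows that dilution of the arm difference would be negligible, and the any-TEAE test carries no margin or decision rule.

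Two stronger readings may tempt a reader:

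- **Every AE with a partial start date becomes a TEAE.** The last two rows of the table show otherwise.
- **A pre-dose AE that worsens on treatment is never counted.** The SAP does not support this. Section 5.6 speaks of an AE that occurs and does not restrict this to onset. Whether a worsening opens a new AE record with its own start date is commonly left to the protocol, which is not at hand. The symptoms listed in Section 5.5.2 are those of the condition under treatment, and nothing in the SAP says they are recorded as AEs starting in screening.

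**Conclusion.** The point holds in a narrow form. For an AE with no start date, or with a partial start in the month or year of first dose, Section 6.1 yields a TEAE even when the recorded stop date shows that it ended before dosing. That conflicts with Section 5.6.

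The consequence is limited to the safety tables, the listings and the any-TEAE comparison of Test with Reference. It is probably small, and its size cannot be calculated because the SAP gives no number of AEs with incomplete start dates. Any stated percentage-point inflation of TEAE incidence would rest on an assumed rate with no source in the document. Equivalence and superiority rest on responder proportions and are unaffected.

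The conflict between the two sections needs no distributional assumption. Its practical relevance assumes that AEs are recorded before first dose. The SAP does not say so outright, but a definition and a date rule that separate AEs by first dose both presuppose it. The correction is worth making because the rule as written gives a demonstrably wrong classification and costs almost nothing to repair.

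**What to change.** Add one sentence to Section 6.1 after the three AE conditions: *An AE with a partial or missing start date is not treatment-emergent if its stop date, or the known part of it, shows that it ended before the date of first dose.*

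In the example, the first three rows of the table would change to not treatment-emergent and the last two would stay as they are. An AE whose stop date is missing, or is too incomplete to show that it ended before first dose, would still be handled by the present conditions, so the conservative convention is kept where real uncertainty remains.

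The cost is one sentence in the SAP and one extra condition in the AE derivation program. No new data are needed. TEAE counts may fall slightly.
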